6.3. Pharmacokinetic Analysis

PK analysis will be performed using the PK population. Additional COVID-19 subgroup analysis for those being impacted by COVID-19 versus those not being impacted may be provided for HM15136 concentrations over time and for HM15136 PK parameters using the descriptive statistical summary table and/or plots. However, unless necessary, the dose proportionality will not be explored for COVID-19 subgroups

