		Week 10	Day 78	Pre-dose 12th dosing
				8 h after 12th dosing
			Day 79	24 h after 12th dosing
			Day 80	48 h after 12th dosing
			Day 81	72 h after 12th dosing
	F/U	OPD	Day 82	96 h after 12th dosing
			Week 13	168 h after 12th dosing
			Week 15	504 h after 12th dosing
			Week 17	840 h after 12th dosing

[PK SAMPLING SCHEDULE] PARTs 1 and 2 - COVID-19 Modification

PK sampling schedule					Time window	Added Time window
Treatment period	OPD	Week 1	Day 1	Pre-dose 1st dosing	-60 min	
				4 h after 1st dosing	±10 min	
			Day 3	48 h after 1st dosing	±30 min	±1 day
			Day 5	96 h after 1st dosing	±30 min	±1 day
		Week 2	Day 8	Pre-dose 2nd dosing	-60 min	
		Week 2	Day 10	48 h after 2nd dosing	±30 min	±1 day
			Day 11	72 h after 2nd dosing	±30 min	±2 days
		Week 3	Day 15	Pre-dose 3rd dosing	-60 min	
			Day 17	48 h after 3rd dosing	±30 min	±1 day
			Day 18	72 h after 3rd dosing	±30 min	±2 days
		Week 4	Day 22	Pre-dose 4th dosing	-60 min	
		Week 5	Day 29	Pre-dose 5th dosing	-60 min	
		Week 6	Day 36	Pre-dose 6th dosing	-60 min	
		Week 7	Day 43	Pre-dose 7th dosing	-60 min	
		Week 8	Day 50	Pre-dose 8th dosing	-60 min	
		Week 9	Day 57	Pre-dose 9th dosing	-60 min	
		Week 10	Day 64	Pre-dose 10th dosing	-60 min	
		Week 11	Day 71	Pre-dose 11th dosing	-60 min	
		Week 12	Day 78	Pre-dose 12th dosing	-60 min	
				4 h after 12th dosing	±10 min	
			Day 80	48 h after 12th dosing	±30 min	±1 day
			Day 82	96 h after 12th dosing	±30 min	±1 day
F/U	OPD	Week 13	Day 85	168 h after 12th dosing	±2 days	
		Week 15	Day 99	504 h after 12th dosing	±2 days	
		Week 17	Day 113	840 h after 12th dosing	±2 days	

[ABBREVIATIONS AND DEFINITIONS]

ABP	Ambulatory blood pressure
ADA	Anti-drug antibody
AE	Adverse event
AESI	Adverse Event of Special Interest
ALP	Alkaline phosphatase
ALT	Alanine aminotransferase
anti-PEG	Anti-polyethylene glycol
AST	Aspartate aminotransferase
AUC	Area under the concentration-time curve
AUC _{%extrap}	Percentage of AUC _{inf} that is due to extrapolation beyond t _{last}
AUC _{0-t}	Area under the concentration-time curve from predose (time 0) to the time of the last quantifiable concentration
AUC _{inf}	Area under the concentration-time curve from predose (time 0) extrapolated to infinite time (AUC _{0-t} + C _{last} /λ ₂)
BMI	Body mass index
BP	Blood pressure
bpm	Beats per minute
BUN	Blood urea nitrogen
CFR	Code of Federal Regulations
CHI	Congenital hyperinsulinism
Cl	Chloride
CL/F	Total body clearance
C _{max}	Maximum concentration
CO ₂	Carbon Dioxide

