6.1.3. Handling of Multiple Observations or Out of Window Observations

Per COVID-19, additional modifications were made to the visit schedule in protocol version 5.0; refer to Table 2 for schedule of events. It was noted that after the protocol amendment, the study might have 2 subjects from Cohort 4 and all subjects from Part 2 that follow the modified visit schedule.

For PK and PD data, if a blood sample was collected outside the protocol specified blood sampling time window, such data will still be included in data analysis, and the actual clock time will be used for PK and PD parameters calculations such as area under the curve. For PD data with multiple observations on the same day and time point, the last observation will be used.

All values, scheduled or unscheduled, will be presented in data listings.

On scheduled visits with missing assessments, unscheduled assessments within the visit window, if available, may be used for analysis. Assessments collected during scheduled visits that are outside the visit window can be used for analysis. A footnote will be added to tables where unscheduled visits are used to impute missing scheduled visits. For vital signs data, if measurements are duplicated within the visit window, the data from the unscheduled visit will be used and the average of the scheduled and unscheduled visits will be taken for summary table. A footnote will be added to table to highlight the exception.

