6.3.3. Dose Proportionality Analysis

Dose proportionality will be assessed using log-transformed PK parameters, AUC_{0-t} at steady state and C_{max} , and a linear regression approach to log-transformed dose levels. The power model will be used to analyze the dose proportionality. The estimate of the ratio of the dose normalized geometric means, R_{dnm} , and the corresponding 90% CI will be derived.

The power model is defined as follows:

$$\log(PK_i) = \alpha + (\beta) * \log(\text{dose}_i) + \mathcal{E}_i$$

Where

PK_i is the PK parameter (C_{max} or AUC_{0-t} at steady state) observation for the subject i .

α is the population intercept.

β is the population slope.

$dose_i$ is the dosage for the subject i .

\mathcal{E}_i is the random error; $\mathcal{E}_i \sim N(0, \sigma^2_{\mathcal{E}})$ and independent.

The assumption for the power model is that the underlying relationship between log(PK parameter) and log(dose) is linear. The dose proportionality corresponds to the ratio of dose normalized geometric means (R_{dnm}), which is defined as ratio of the predicted geometric mean of the highest dose relative to the predicted geometric mean of the lowest dose. The dose proportionality would be declared when the 90% CI for the R_{dnm} falls entirely within the limit of 0.8 to 1.25.

Log(PK parameter) and log(dose) will be plotted in a line plot for AUC_{0-t} at steady state and C_{max} .

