		Week 11	Day 71	Pre-dose 11th dosing	
F/U	In-house Period 2	Week 12	Day 78	Pre-dose 12th dosing 8 h after 12th dosing	
			Day 79	24 h after 12th dosing	
			Day 80	48 h after 12th dosing	
			Day 81	72 h after 12th dosing	
			Day 82	96 h after 12th dosing	
		Week 13	Day 85	168 h after 12th dosing	
		Week 15	Day 99	504 h after 12th dosing	
		Week 17	Day 113	840 h after 12th dosing	
				±2 days	
				±2 days	
				±2 days	

PK Sampling Schedule (Parts 1 and 2) – COVID-19 Modification

PK sampling schedule				Time window	Added Time window	
Treatment period	OPD	Week 1	Day 1	Pre-dose 1st dosing	-60 min	
				4 h after 1st dosing	±10 min	
			Day 3	48 h after 1st dosing	±30 min	±1 day
			Day 5	96 h after 1st dosing	±30 min	±1 day
		Week 2	Day 8	Pre-dose 2nd dosing	-60 min	
		Week 2	Day 10	48 h after 2nd dosing	±30 min	±1 day
			Day 11	72 h after 2nd dosing	±30 min	±2 days
		Week 3	Day 15	Pre-dose 3rd dosing	-60 min	
			Day 17	48 h after 3rd dosing	±30 min	±1 day
			Day 18	72 h after 3rd dosing	±30 min	±2 days
		Week 4	Day 22	Pre-dose 4th dosing	-60 min	
		Week 5	Day 29	Pre-dose 5th dosing	-60 min	
		Week 6	Day 36	Pre-dose 6th dosing	-60 min	
		Week 7	Day 43	Pre-dose 7th dosing	-60 min	
		Week 8	Day 50	Pre-dose 8th dosing	-60 min	
		Week 9	Day 57	Pre-dose 9th dosing	-60 min	
		Week 10	Day 64	Pre-dose 10th dosing	-60 min	
		Week 11	Day 71	Pre-dose 11th dosing	-60 min	
F/U	OPD	Week 12	Day 78	Pre-dose 12th dosing	-60 min	
				4 h after 12th dosing	±10 min	
			Day 80	48 h after 12th dosing	±30 min	±1 day
			Day 82	96 h after 12th dosing	±30 min	±1 day
		Week 13	Day 85	168 h after 12th dosing	±2 days	
		Week 15	Day 99	504 h after 12th dosing	±2 days	
		Week 17	Day 113	840 h after 12th dosing	±2 days

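### Cmax and steady-state AUC come from two non-comparable sampling grids, and the dose-proportionality model has no pre-specified check where one Part mixes them

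*SAP*

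**What the plan says.** **The two grids.** The standard PK sampling schedule (Protocol, PK Sampling Schedule; SAP Appendix, Table 3) has a full profile after doses 1 and 12, with samples such as "8 h after 12th dosing", "24 h after 12th dosing" and "72 h after 12th dosing". The COVID-19 modification drops those three times from both profiles, adds "4 h after 12th dosing" (and the same after dose 1), and allows an extra ±1 day at 48 h and 96 h. It keeps samples such as "72 h after 2nd dosing", but only after doses 2 and 3.

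**The analysis.** SAP 6.3.2 summarises PK parameters by cohort/dose level. SAP 6.3.3 then states: "Dose proportionality will be assessed using log-transformed PK parameters, AUC" at steady state and Cmax, regressed on log dose. Proportionality is declared if the 90% CI for R_dnm lies within 0.8 to 1.25. The model has no schedule term. SAP 6.1 keeps Parts 1 and 2 separate.

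**What is offered on schedule.** SAP 6.3 permits, but does not require, descriptive summaries of concentrations and PK parameters for subjects affected or not affected by COVID-19. For proportionality it says "unless necessary, the dose proportionality will not be explored for COVID-19 subgroups". No analysis on common sampling times is specified.

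**Who is affected.** SAP 6.1.3 says the study might have "2 subjects from Cohort 4 and all subjects from Part 2 that follow the modified visit schedule".

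**The concern.** Cmax is the largest sampled concentration and AUC is built from the sampled points, so the same subject can get different values under the two grids with no change in pharmacokinetics. Using actual clock times, as SAP 6.1.3 does, corrects AUC for late or early draws but cannot recover a peak that nobody sampled.

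If a Part contains both grids and their mix differs between dose groups, the difference enters the slope and hence R_dnm. Cmax and AUC are primary PK endpoints, and these two carry a formal acceptance rule.

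The text does not show where mixing occurs. Cohort 4 belongs to Part 2, so naming two of its subjects in addition to all of Part 2 makes no sense as written. The two may have been meant as Part 1 subjects: the version 5.0 amendment summary, used here only as context, names Cohort 3. Or only two Cohort 4 subjects may have been on the modified grid; the same summary says Cohort 4 subjects were already enrolled and dosed at that amendment. The two readings have very different consequences.

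**Working it through.** The plan gives no PK precision figure or sample-size calculation, so there is no stated number to reproduce.

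**Step 1: compare the grids after doses 1 and 12.** Standard {0, 8, 24, 48, 72, 96, 168} h; COVID {0, 4, 48, 96, 168} h. Dropped: 8, 24, 72 h. Added: 4 h. Shared: 0, 48, 96, 168 h.

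**Step 2: effect on Cmax and AUC.** Assumptions, since the documents give half-life only for animals (26.6-56.2 h, Protocol 3.4) and no human Tmax: one compartment with first-order absorption, twelve weekly doses, half-life 36, 56, 80, 120 or 160 h, single-dose Tmax 12-72 h where the model allows it. AUC is taken over 0-168 h with the linear-up, log-down rule of SAP 6.3.2. COVID/standard ratios at nominal times after dose 12:

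| Single-dose Tmax | Cmax ratio | AUC0-168 ratio |
|---|---|---|
| 12-24 h | 0.66-0.92 | 0.86-0.99 |
| 36 h | 0.96-0.99 | 0.91-0.97 |
| 48 h or later | 1.00 | 0.95-0.98 |

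The lowest Cmax ratio is at half-life 36 h, Tmax 16 h. Observed Tmax typically moves from 24 h to 48 h when the true peak is at about 16-36 h. With half-life 36-120 h and Tmax 16-72 h, moving the 48 h and 96 h draws by up to a day widens the ranges to 0.51-1.00 (Cmax) and 0.75-0.99 (AUC).

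**Step 3: effect on R_dnm.** R_dnm = (highest dose / lowest dose)^(β − 1). With two dose groups, or three equally spaced log doses of equal size, the slope depends only on the end groups. For a truly proportional drug,

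R_dnm = r^(f_top − f_bottom),

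where r is the COVID/standard ratio and f the fraction of a group on the COVID grid. Taking r = 0.80 for Cmax:

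- Part 1 (0.02, 0.04, 0.08 mg/kg; 9 each), 2 of 9 top-dose subjects on the COVID grid: 0.80^(2/9) = 0.95.
- Part 2, every profile on the COVID grid: 0.80^(1 − 1) = 1.00.
- Part 2, Cohort 4 (0.06 mg/kg, 15 active) all standard and Cohort 5 (0.02 mg/kg, 9 active) all COVID: 0.80^(0 − 1) = 1.25.
- Same, with 2 of the 15 in Cohort 4 on the COVID grid: 0.80^(2/15 − 1) = 0.80^(−13/15) = 1.21.

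These use planned group sizes and the ceiling doses of Cohorts 3 and 5. The Part 2 cases assume that optional Cohorts 6 and 7 are not run.

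**Step 4: against the width of the interval.** At an assumed CV of 30%, the SD of log Cmax is √ln(1 + 0.30²) = 0.294. The 90% CI around R_dnm = 1 is then 0.79-1.27 in Part 1 (25 df) and 0.81-1.24 in Part 2 with Cohorts 4 and 5 only (22 df). Shifting the Part 2 interval by 1.21 gives 1.21 × 0.81 = 0.98 to 1.21 × 1.24 = 1.50, outside the limit.

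**Step 5: after restriction to shared times.** Deriving both parameters from 0, 48, 96 and 168 h for everyone makes the between-grid ratio 1.00 at nominal times by construction, so the grid contribution to R_dnm disappears apart from scatter from the ±1 day windows.

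**The case against.** The strongest reply is that the Parts are never pooled. Read literally, SAP 6.1.3 puts all of Part 2 on one grid, where the artefact is nil, and leaves few or no affected subjects in Part 1, where the shift is small. At 30% CV the Part 1 interval already overruns 0.8-1.25 with no schedule effect, so a move to 0.95 would seldom change a declaration. The Cmax effect vanishes for a late peak. SAP 6.3 does allow descriptive summaries by COVID-19 impact, and Protocol 11.2.7 allows additional analysis after data review.

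Most of this stands. It does not close the point: the literal reading relies on a sentence that cannot be right as written, the COVID-19 schedule is permissive rather than mandatory, and Cohort 5 was allowed to overlap Cohort 4. AUC is lower on the COVID grid in every modelled case, late peak or not. An optional descriptive table does not correct R_dnm.

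A reader might infer more: that grid and dose are known to be confounded, that Part 1 R_dnm falls by the full Cmax ratio, or that Tmax is also tested. The documents support none of these. No text puts the whole top-dose group of Part 1 on the modified grid, the plan says only that subjects might follow it, and Tmax never enters the power model.

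**Conclusion.** The point holds conditionally. The grids do not give comparable Cmax and AUC, and no schedule-matched proportionality analysis is pre-specified. Bias in R_dnm arises only in a Part that mixes grids, and the documents cannot settle whether one does.

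At a Cmax ratio of 0.80 the consequence runs from nothing (Part 2 on one grid), through a minor shift to 0.95 (Part 1, 2 of 9), to 1.21-1.25 (Part 2, Cohort 4 mostly or wholly standard against Cohort 5 modified). Only the last would by itself be likely to decide the declaration. These sizes rest on an assumed model, half-life, Tmax and CV; if human Tmax is 48 h or later, the nominal-time Cmax effect is nil and only the AUC difference remains. This is a worthwhile low-cost improvement, not evidence that the planned result is wrong.

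**What to change.** 1. Correct SAP 6.1.3. Classify each Day 1 and Day 78 PK profile by the grid actually followed and give counts per cohort. Classifying profiles rather than subjects also exposes any accumulation ratio (SAP 3.1.2) that compares a standard Day 1 with a modified Day 78.
2. In SAP 6.3 and 6.3.3, replace the open-ended exemption with a pre-specified sensitivity power model, run wherever a Part mixes grids. Derive Cmax and AUC for every subject from the shared nominal times (0, 48, 96, 168 h), using actual clock times, and report it beside the all-samples result.
3. Tabulate Cmax and Tmax by grid, descriptively only.

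The cost is one extra non-compartmental run and a few tables. The limits are real: a common-time Cmax misses any early peak for everyone, a common-time AUC understates exposure for everyone, and the ±1 day windows leave residual scatter. It should therefore stand as a sensitivity analysis, not a replacement for the main model.

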6.3.1. HM15136 Pharmacokinetic Concentration Analysis

The concentration-time data of HM15136 will be summarized descriptively by cohort/dose level. Two line plots for mean concentration +/- standard deviation over time, one on original raw scale and the other on the logarithm scale, will be generated for the PK population with cohort/dose level overlaid. Graphical analysis using line plots of individual profiles will also be performed.

6.3.2. HM15136 Pharmacokinetic Parameter Analysis

The non-compartmental PK parameters of HM15136 will be summarized descriptively by cohort/dose level. AUC parameters, AUC_{0-t} at steady state and C_{max} , will be log-transformed and geometric statistics will be included. Graphical analysis using box plots for PK parameters of AUC_{0-t} at steady state and C_{max} will be performed. To calculate AUC, for the absorption phase, the linear rule will be used; and for the elimination phase, the logarithmic rule will be used.

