6.3. Rationale of Trial Design

6.3.1. Selection of subjects in test group

Part 1 in this study is to administer HM15136 once a week for a total of 12 weeks to subjects who are obese or overweight with comorbidities. All cohorts in Part 2 will receive HM15136 once a week for a total 12 weeks for subjects who have type 2 DM among the obese or overweight with comorbidities.

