6.3.3. Rationale of initiation and maximum dosage adjustments

A dose of 0.01, 0.02, 0.03, 0.05, 0.08, 0.10, or 0.12 mg/kg was given to HM-GCG-101, a single-dose study of HM15136 in healthy volunteers. In general, assuming that the clearance rate is the same for each dose, the AUC (AUC_{168ss}) value for 1 week in the steady state after repeated administration is equal to the AUC_{inf} value when the same dose is administered once.

The planned maximum dose for this study is 0.08 mg/kg. The maximum AUC_{inf} observed in the single dose study (HM-GCG-101) administered at this dose was 60,772 ng·h/mL. In addition, when the NOAEL of 0.5 mg/kg (human equivalent dose 0.08 mg/kg) in the rat 13-week toxicity evaluation (2018-0265) was repeatedly administered, the most conservative AUC_{0-168h} value was 98,300 ng·h/mL at the 13th week. The safety margin of the maximum therapeutic dose of 0.08 mg / kg is approximately 1.6 times the most conservative value of the 13-week AUC_{0-168h} (98,300 / 60,772) in the NOAEL of the rat toxicity assessment at the 13th week.

The planned starting dose for this study is 0.02 mg/kg. This was calculated in reverse order to achieve the maximum planned capacity (0.08 mg/kg) assuming a maximum two-fold of the three planned cohorts, and was also selected by considering the minimum effective capacity (ED₁₀) value in the weight loss potency test (Dv-8088, E2018242) conducted in rats and mice (In the weight loss efficacy test of rats and mice, ED₁₀ was 0.012 and 0.014 mg/kg respectively converted to equivalent human dose).

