10.3. Endpoints**10.3.1. Primary endpoints**

To assess safety and tolerability of HM15136 after repeated subcutaneous (SC) doses for 12 weeks.

- Incidence of adverse events (AEs):
cardiovascular (CV) events, rash/inflammatory dermatitis and other skin disorders, gastrointestinal (GI) events, and gallstone formation (cholelithiasis) will be managed following separate AE guidance document of HM15136 [Appendix].
- Incidence of clinical lab abnormalities:
including serum amylase, serum lipase, coagulation, thyroid stimulating hormone (TSH), serum calcitonin. Only for female, LH (Luteinizing hormone) and FSH (follicle stimulating hormone) are additionally included.
- Immunogenicity:
Anti-drug antibodies (ADAbs), neutralizing antibodies (nAbs), anti-polyethylene glycol antibodies (anti-PEG)
- Incidence and severity of clinical findings on physical examination
- Change from baseline in vital signs:
Supine position blood pressure (BP), heart rate (HR), respiratory rate, and tympanic temperature
- Changes of blood pressure (BP) and heart rate:
BP assessed by 24-hour ambulatory blood pressure monitoring (ABPM);
HR assessed by 24-hour ambulatory electrocardiography monitoring (Holter ECG; central reader)
- Change from baseline in 12-lead ECG parameters:
the primary ECG endpoint will be QTcF
- Injection site reactions

To assess the pharmacokinetic (PK) profile of HM15136 after administration of repeated subcutaneous (SC) doses in obese subjects by, but not limited to:

- C_{max} : Maximum concentration
- T_{max} : Time to reach C_{max}
- C_{trough} : Trough serum concentration
- AUC: Area under the concentration-time curve

Ex.) AUC_{0-t} : AUC at steady state during the period of injection (AUC_{0-t} at steady state)

- K_{el} : Terminal elimination rate constant
- $t_{1/2}$: Terminal half-life
- CL/F: Apparent clearance
- V_z/F : Apparent volume of distribution

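### SAP 6.3.2 and 6.3.3 do not say where the steady-state AUC stops, and the protocol's two descriptions of AUC0-t conflict; under one of them the integration interval can lengthen with dose

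*SAP*

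**What the plan says.** SAP 6.3.2 names the AUC for the log-scale summary and box plots: "AUC_{0-t} at steady state and C_{max} , will be log-transformed and geometric statistics will be included". SAP 6.3.3 puts the same parameter into the power model, as each "observation for the subject", and declares proportionality if the 90% CI for the dose-normalised ratio of highest to lowest dose lies within 0.8 to 1.25. SAP 3.1.2 lists AUC0-t and AUCinf without defining either. The SAP nowhere names an AUC over the dosing interval.

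The protocol has two descriptions of AUC0-t:

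- Abbreviations and Definitions: "Area under the concentration-time curve from predose (time 0) to the time of the last quantifiable concentration".
- Study Summary and 10.3.1: "AUC at steady state during the period of injection", with no hours given.

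An explicit one-week steady-state AUC appears only in the dose rationale, Protocol 6.3.3, where the "value for 1 week in the steady state after repeated administration is equal to the" single-dose AUCinf if clearance is constant.

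Three other provisions matter:

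- Protocol 6.3.1 has Part 1 "administer HM15136 once a week for a total of 12 weeks", so the dosing interval is 168 h.
- The PK sampling schedule (SAP appendix) follows the 12th dose at 168 h (Day 85), 504 h (Day 99) and finally "840 h after 12th dosing" (Day 113), each with a window of ±2 days.
- SAP 6.1.5 sets concentrations below the quantitation limit to missing, and SAP 6.1.3 calculates AUC from actual clock times.

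**The concern.** After a single dose, integrating to the last quantifiable sample is routine. After the last dose of a weekly regimen, with sampling for five weeks, it is no longer an interval AUC. It can cover one, three or five dosing intervals, depending on when the subject's concentrations fall below the assay limit. Higher doses stay above that limit longer, so the upper limit of integration can depend on dose. That dependence would enter the power-model slope as apparent non-proportionality, even for a drug that is exactly proportional.

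AUC is a primary PK endpoint and one of the two parameters in the proportionality test. With t left open, two analysts following these documents could get different answers, and the interval could be chosen after the concentrations have been seen.

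**Working it through.** **The plan's own figure.** The one stated figure that rests on a weekly steady-state AUC is the exposure margin in Protocol 6.3.3: 98,300 / 60,772 = 1.62, given as about 1.6. It reproduces. The sampling times agree as well: (85 − 78) × 24 = 168 h, (99 − 78) × 24 = 504 h, (113 − 78) × 24 = 840 h.

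**Assumptions that the documents do not supply.** One compartment, first-order absorption with a half-life of 12-24 h, linear kinetics, and a human elimination half-life of 40-100 h in the main run. Protocol 3.4 gives only animal half-lives, 26.6-56.2 h. Cohort 3 is taken at its ceiling of 0.08 mg/kg.

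**Model.** Single-dose concentration is proportional to ka/(ka − ke) × (exp(−ke·t) − exp(−ka·t)). The AUC from 0 to T after dose 12 adds this curve over 12 doses given 168 h apart. Ratio to AUC0-168 after dose 12:

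| Upper limit T | Half-life 56 h | Half-life 72 h | Half-life 100 h |
|---|---|---|---|
| 168 h | 1.00 | 1.00 | 1.00 |
| 504 h | 1.18-1.24 | 1.29-1.35 | 1.47-1.54 |

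A hand check that ignores absorption: with q = 2^(−168/half-life), the tail beyond 168 h as a fraction of the interval AUC is q/(1 − q). At 56 h, q = 2^(−3) = 0.125 and the tail is 0.125/0.875 = 0.143. At 72 h, q = 0.198 and the tail is 0.248. Slow absorption raises both, as in the table.

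**Effect on the power model.** Doses 0.02, 0.04 and 0.08 are equally spaced on the log scale, so the middle dose has no leverage on the slope. If only the top dose is integrated to 504 h, with ratio b to AUC0-168, then β = 1 + ln(b)/ln(4), and the top-to-bottom dose-normalised ratio is 4^(β − 1) = b. The table entries are therefore the bias itself.

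**When the last quantifiable time differs by dose.** Exposure was scaled so that single-dose AUCinf at 0.08 mg/kg is 60,772 ng·h/mL. Absorption half-life was 24 h, the original sampling schedule was used, and quantitation limits of 0.5-50 ng/mL were tried:

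| Half-life | Ratio with t = last quantifiable sample |
|---|---|
| 27-40 h | 1.00 up to 20 ng/mL; 1.27-1.38 at 50, because the low dose stops at 96 h |
| 56 h | 1.24 at 1-2 ng/mL; 1.00 at 0.5 and at 5-20; 1.47 at 50 |
| 72 h | 1.35 at 5 ng/mL; 1.00 at the other limits tried |

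Over half-lives of 27-150 h and both sampling schedules the range is 1.00 to 1.81. With AUC fixed at 0-168 h and a fully quantifiable 168 h profile, the ratio is 1.00 throughout.

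**Effect on the 0.8-1.25 criterion.** Three doses with 9 active subjects each, 90% CI, drug truly proportional, between-subject CV assumed:

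| CV | No bias | Bias 1.14 | Bias 1.25 |
|---|---|---|---|
| 15% | 85% | 36% | 5% |
| 20% | 51% | 23% | 5% |
| 30% | about 5% | 3% | 1% |

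**Stopping at the actual Day 85 sample.** The window allows 120-216 h. For half-lives of 40-100 h, AUC to 120 h is 0.77-0.89 of AUC0-168, and AUC to 216 h is 1.05-1.17 of it. No link between visit timing and dose is stated, so this is added variation rather than slope bias.

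**The case against.** The strongest reply is that the endpoint section governs the parameter, and the SAP repeats its steady-state label. For a weekly drug, the injection period reads naturally as the dosing interval, and the dose rationale also uses a one-week steady-state AUC. If the subscript was meant as tau, the intended quantity is already right. This stands in part: a reader might infer that the protocol simply prescribes the wrong AUC, and the documents do not support that. They conflict. But the endpoint wording gives no hours, and the abbreviation list defines AUC0-t in words. The same list builds AUCinf as AUC0-t plus an extrapolated tail, which requires t to be the last quantifiable time. Protocol 11.2.7 also pairs AUC0-t with AUCinf for dose proportionality. An analyst could reasonably follow either description.

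The size can also be challenged. At 56 h, the longest animal half-life, the ratio of 1.18-1.24 lies inside 1.25 as a point estimate, and many scenarios show no bias. That is correct. However, the criterion applies to the whole 90% CI, so a ratio well short of 1.25 already lowers the chance of meeting it.

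A reader might go further and infer that the accumulation ratio is inflated, or that CL/F is wrong because AUCinf after dose 12 carries over earlier doses. SAP 3.1.2 only lists these parameters. It gives no formula for the accumulation ratio, does not say that AUCinf is derived after dose 12, and does not tie CL/F to it. Those errors cannot be attributed to the plan. Nor does any section plan to recompute the 1.6 margin from this AUC.

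Finally, at a CV near 30% with 9 per dose the criterion is rarely met even without bias. Fixing the interval removes a possible bias but not that imprecision.

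**Conclusion.** The concern holds as an unresolved definition. The SAP does not state the upper limit of the AUC behind its exposure summary and proportionality test, and the protocol's two descriptions lead to different quantities. If AUC is taken to the last quantifiable sample after dose 12, and the 504 h sample is quantifiable only at the top dose, an exactly proportional drug shows a ratio of about 1.18-1.24 at a 56 h half-life or 1.29-1.35 at 72 h. If the last quantifiable sample is the same at every dose, the ratio is 1.00.

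These sizes rest on the assumed one-compartment model and on a human half-life and quantitation limit that the documents do not give. The direction, an interval that can lengthen with dose, follows from the sampling schedule, the handling of values below the limit and the abbreviation-list definition. Simply stopping at the Day 85 sample is not enough, because it leaves variation of about 0.77-1.17 times AUC0-168 at the extremes of the window.

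**What to change.** - In SAP 3.1.2, 6.3.2 and 6.3.3, define the parameter as AUC over 0-168 h at steady state after the 12th dose. Interpolate, or extrapolate with Kel, to exactly 168 h from actual sampling times. State what is done when the 168 h sample is below the quantitation limit.
- Reconcile the protocol's abbreviation list with its endpoint section so that one definition remains.
- Use the 504 h and 840 h samples only for Kel and half-life.
- As a clarification, state that CL/F at steady state is dose divided by AUC(0-168h), and that the accumulation ratio is AUC(0-168h) after dose 12 over AUC(0-168h) after dose 1.
- SAP section 1 says that the Part 1 database is already locked. Check how its AUC was derived, report it, and rederive if a different interval was used. Fix the definition for Part 2 before unblinding.

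The cost is SAP wording and a software setting, with no new samples. The one drawback is some reliance on Kel extrapolation when the Day 85 sample is early or below the limit; the number of such profiles should be reported.
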